#### **DATA ANALYSIS:**

Rotational stability of the IOL will be evaluated by measuring axis misalignment, which is defined as the absolute difference between intended IOL axis of orientation (immediately at the end of the surgery) and follow-up visit(s) as measured by a photographic based method. For the primary endpoint the percentage of eyes with  $\leq 5^\circ$  of axis misalignment from the intended IOL axis of orientation at the 1-week postoperative visit along with the 95% confidence interval will be

reported. The percent of eyes with misalignments  $\leq 5^\circ$ ,  $< 10^\circ$ ,  $< 20^\circ$  and  $>30^\circ$  will also be reported for all other postoperative timepoints (1-day and 3-months).

For visual acuity and refractive data, descriptive statistics will include the mean, standard deviation, median, minimum and maximum. For visual acuity, the frequency and proportion of eyes achieving each acuity line will also be reported. The frequency and proportion of eyes within 0.5 D and within 1.0 D of intended values will also be determined for postoperative refractive cylinder and spherical equivalent.

For questionnaire data, the frequency and proportion with each rating for each item will be reported. In addition, the frequency and proportion of eyes with medical findings, lens findings, complications and adverse events will also be reported.

### **STUDY VISITS AND PROCEDURES:**

Subject eligibility will be assessed at the preoperative visit according to the inclusion/exclusion criteria. The ICF and HIPAA must be signed by any patients who agree to participate in the study prior to undergoing any study-specific procedures. This will include designation as to whether one or both eyes are to be included in the study. Those subjects who meet the inclusion/exclusion criteria and agree to participate will be implanted in one or both eyes with the study lens. All subjects are intended to have either unilateral or bilateral cataract surgery with the second-eye surgery occurring no more than 30 days after the first eye surgery.

Key preoperative data include ocular health and history, pupil measurement, visual acuities, keratometry, intraocular pressure (IOP), biomicroscopic slit lamp findings, fundus exam findings and biometry. The operative visit will include standard procedures for cataract surgery and IOL implantation as well as photographic image of the IOL position, slit lamp exam, complications and adverse event assessment. Key postoperative data include photographic image of the IOL position, manifest refraction, uncorrected distance visual acuity (UCDVA), best-corrected distance visual acuity (BCDVA), Slit Lamp findings, non-directed visual symptoms, 2-item Patient Satisfaction Questionnaire (PSQ), 3-item Investigator Satisfaction Questionnaire (ISQ) and adverse events. The PSQ will only be administered on subjects bilaterally implanted with the study lens.

## **2. BACKGROUND/INTRODUCTION**

Approximately a third of patients presenting for cataract surgery are likely to have at least 1.0 D of corneal astigmatism. Patients with astigmatism that desire spectacle independence after cataract

---

surgery will need a method to eliminate or reduce corneal cylinder. Kessel et. Al., compared the two most commonly available options to reduce astigmatism and noted that the most effective way to reduce astigmatism is by implanting a toric IOL. For toric IOLs to be effective, IOL rotation after implantation must be minimal; it has been noted that as little as 1 degree of rotation can result in 3.3% reduction in the toric lens effectiveness in reducing astigmatism.

JJSV has developed a new IOL platform designed to minimize rotation to  $\leq 5^\circ$  within the first week after implantation. The TECNIS® Toric II 1-Piece lens is an ultraviolet light-absorbing posterior chamber intraocular lens (IOL) that compensates for corneal spherical aberrations and corneal astigmatism. The benefits of aspheric compensation for corneal spherical aberrations are contingent upon full refractive correction of sphere and cylinder. The IOLs incorporate a proprietary wavefront-designed toric aspheric optic with a squared posterior optic edge designed to provide a 360° barrier. The edge of the optic has a frosted design to reduce potential edge glare effects. In addition, compared to the TECNIS Toric 1-Piece IOL, the haptics of the TECNIS Toric II 1-Piece IOLs have a squared and frosted design. The anteriorly located cylinder axis marks denote the meridian with the lowest power and is to be aligned with the steep corneal meridian.

### 3. CLINICAL HYPOTHESIS

TECNIS Toric II IOL will demonstrate excellent rotational stability by demonstrating  $\leq 5^\circ$  of axis misalignment from the intended IOL axis of orientation in 90% of the eyes at the 1-week postoperative visit.

### 4. STUDY DESIGN

This is a prospective, multicenter, single-arm, open-label clinical study of the commercially available TECNIS Toric II IOL. The study will be conducted in up to 192 subjects needing unilateral or bilateral cataract surgery in up to 8 sites in United States (US). The subjects will be followed for up to 3-months postoperatively.

### 5. ACRONYMS

The following acronyms are used throughout this document:

- ADE: adverse device effect
- AK: astigmatic keratotomy
- BCDVA: best-corrected distance visual acuity
- BSS: balanced salt solution
- CRF: case report form

---

- CRI: corneal relaxing incisions
- D: diopters
- DFU: directions for use
- EDC: electronic data capture
- GCP: good clinical practice
- HIPAA: health insurance portability and accountability act
- ICF: informed consent form
- IOL: intraocular lens
- IOP: intraocular pressure
- IRB: institutional review board
- ISQ: investigator satisfaction questionnaire
- LASIK: laser-assisted in-situ keratomileusis
- LASEK: laser epithelial keratomileusis
- LRI: limbal relaxing incisions
- OCCl: opposite clear corneal incisions
- OR: operating room
- PRK: photorefractive keratectomy
- PSQ: patient satisfaction questionnaire
- SAE: serious adverse events

- UCDVA: uncorrected distance visual acuity
- UADE: unanticipated adverse device effect
- USADE: unanticipated serious adverse device effect

## 6. STUDY OBJECTIVES AND ENDPOINTS

The purpose of this clinical study is to evaluate the rotational stability of the TECNIS® Toric II IOL. Primary endpoint is percentage of eyes with  $\leq 5^\circ$  axis misalignment from the intended IOL axis of orientation at the 1-week postoperative visit.

The final 3-month visit will be the key timepoint for visual acuity, manifest refraction and patient and investigator reported outcomes questionnaire evaluations. Other timeframes will be provided as supportive analysis.

### 6.1 PRIMARY ENDPOINT

The primary endpoint for the study is the percentage of eyes with  $\leq 5^\circ$  axis misalignment from the intended IOL axis of orientation at the 1-week postoperative visit. Rotational stability of the IOL will be evaluated by measuring axis misalignment, which is defined as the absolute difference between intended IOL axis of orientation (immediately at the end of the surgery) and follow-up visit(s) as measured by a photographic based method.

### 6.2 OTHER ENDPOINTS

- Residual mean manifest cylinder and spherical equivalent for all eyes
- Percentage of eyes that achieve UCDVA of 20/40, 20/32, 20/25 & 20/20
- Percentage of eyes that achieve accuracy of cylinder (to target):
  - within:  $\pm 0.50$  D and  $\pm 1.00$  D
- Analysis of lens axis misalignment (compared to target) including:
  - Mean absolute and signed value of the misalignment
  - Percentage of eyes with lens axis misalignments  $\leq 5^\circ$ ,  $< 10^\circ$ ,  $< 20^\circ$  and  $>30^\circ$
- Medical findings/Lens findings/Complications
- Subject responses on Patient Satisfaction Questionnaire (PSQ)

**NOTE:** Should be administered only in subjects who have been implanted with the study lens bilaterally

- Investigator responses on Investigator Satisfaction Questionnaire (ISQ)
- Adverse event rates including the rate of IOL repositioning and/or IOL exchange primarily due to IOL misalignment.

## 7. STUDY PRODUCTS

### 7.1 INTRAOCULAR LENSES

The TECNIS® Toric II IOL (study lens), Models ZCU150, ZCU225, ZCU300, ZCU375, ZCU450, ZCU525, and ZCU600 are posterior chamber, 1-piece, aspheric, hydrophobic acrylic foldable IOLs and are to be implanted in the capsular bag following cataract extraction. It is designed to minimize the occurrence of large rotations (greater than 10°) following implantation.

The TECNIS Toric II is a UV light-absorbing posterior chamber lens that compensates for corneal spherical aberrations and corneal astigmatism. The benefits of aspheric compensation for corneal spherical aberrations are contingent upon full correction of spherical (defocus) and cylindrical (astigmatic) refractive error.

The TECNIS Toric II incorporates an aspheric optic with a squared posterior optic edge designed to provide a 360° barrier for reducing the incidence of posterior capsular opacification (PCO). The visual benefits of the proprietary wavefront-designed aspheric optic have been clinically assessed using the TECNIS Z9000 IOL (under Investigational Device Exemption G960221). As featured in the currently marketed TECNIS Toric (ZCT Series) design, the edge of the optic is frosted to reduce potential for edge glare effects.

The TECNIS Toric II IOLs have two sets of four axis orientation marks 180° apart in the outer periphery of the anterior optic surface to indicate the meridian of the lowest power (flat meridian). These axis orientation marks are for proper alignment of the flat meridian of the IOL with the steep meridian of the corneal curvature.

The ZCU150, ZCU225, ZCU300, ZCU375, ZCU450, ZCU525, and ZCU600 lens models are intended for cataract patients with pre-existing corneal astigmatism that, when taking surgically induced astigmatism into account, have approximately 0.75 D to 4.75 D of predicted corneal astigmatism to be corrected (**Table 1**).

**TABLE 1: TECNIS® Toric II Models ZCU, IOL Astigmatism Correction Range**

	Cylinder Powers (D)						
IOL Model	ZCU150	ZCU225	ZCU300	ZCU375	ZCU450	ZCU525	ZCU600
IOL Plane (Labeled)	1.50	2.25	3.00	3.75	4.50	5.25	6.00
Corneal Plane*	1.03	1.54	2.06	2.57	3.08	3.60	4.11

\*The corresponding cylinder values at the corneal plane have been calculated based on the average pseudophakic eye.

**Table 2** lists the general design characteristics of the TECNIS Toric II IOLs.

**TABLE 2: Lens Characteristics of the TECNIS® Toric II Model ZCU**

CHARACTERISTICS	TECNIS Toric II IOL (Model ZCU)
Lens Design	1-piece acrylic biconvex monofocal IOL with aspheric toric anterior curvature
Lens Material	Surface-treated SENSAR® soft acrylic (acrylic with covalently bound UV absorber), AMOS3225
Overall Diameter	13.0 mm
Optical Center Thickness	0.722 mm (20.0 D Lens)
Haptic Angle	No angulation, but offset from the optic body
Optic Body Diameter	6.0 mm
Haptic Material	Same as optic
Haptic Width	0.39 mm
Haptic Thickness	0.46 mm
Haptic Style	C-loop
Other features	Axis orientation marks
Optic Shape	Biconvex
Anterior Optic Profile	Aspheric with a maximum and a minimum radii of curvature perpendicular to each other
Posterior Optic Profile	Spherical
Optic Edge Design	PROTEC™ squared edge
Dioptric Power Range	+5.0 to +34.0 D in 0.50 D increments
Cylinder Power Range	1.50 D, 2.25 D, 3.00 D, 3.75 D, 4.50 D, 5.25 D, and 6.00 D (at the IOL plane)
Refractive Index	1.470 (35° C)

CHARACTERISTICS	TECNIS Toric II IOL (Model ZCU)
Asphericity of Lens	-0.27 um
Theoretical A-constant a	118.8 for ultrasound biometry, 119.3 for optical biometry

a For lens power calculations, the investigator's personalized A-Constant for the TECNIS Toric ZCU IOLs are to be used.

## INDICATION

The TECNIS® Toric II 1-Piece posterior chamber lenses are indicated for the visual correction of aphakia and pre-existing corneal astigmatism of one diopter or greater in adult patients with or without presbyopia in whom a cataractous lens has been removed by phacoemulsification and who desire improved uncorrected distance vision, reduction in residual refractive cylinder, and increased spectacle independence for distance vision. The device is intended to be placed in the capsular bag.

## 7.2 IMPLANTATION SYSTEMS

JJSV recommends using The UNFOLDER® Platinum 1 Series Implantation System (the 1MTEC30 Cartridge and the DK7796 inserter). Alternate validated insertion systems that can be used to insert the TECNIS Toric II 1-Piece lens include the UNFOLDER® EMERALD-AR Series Implantation System (with the 1CART30 Cartridge), the ONE SERIES Ultra Insertion System (the 1VPR30 Cartridge and the DK7786 or DK7791 inserters) or any other Johnson & Johnson Surgical Vision, Inc.-qualified insertion system. Only insertion instruments that have been validated and approved for use with this lens should be used. Please refer to the DFU for the insertion instrument or system for additional information.

## 8. STUDY POPULATION

All study subjects will be enrolled from the normal surgical cataract population at up to 8 sites in the U.S. Up to 192 subjects (116 bilateral and 76 unilateral) will be enrolled to achieve approximately 200 eyes available for analysis at 1-week with a target of 75% of the eyes coming from bilateral subjects and 25% of the eyes coming from unilateral subjects. This accounts for screen failures, drop-out rate and unanalyzable photographs for toric IOL rotation analysis. Each site should implant approximately 24 subjects and no site may implant more than 25% of the enrollment total.

This study will include subjects undergoing unilateral and bilateral primary cataract extraction and IOL implantation and who meet all the study inclusion and exclusion criteria in one or both eyes. Subjects who meet the eligibility criteria will be offered enrollment in the study. Eligibility criteria may not be waived by the investigator. Any questions regarding patient eligibility are to be discussed with JJSV prior to subject enrollment. Those subjects who meet the eligibility criteria and agree to participate will receive the TECNIS Toric II IOL Model ZCU in one or both eyes.

Subjects will be enrolled at each site sequentially until the overall study recruitment goals are met or the site limit is reached.

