### **21.1 ANALYSIS POPULATION**

For monocular endpoints, all eyes implanted with a study toric IOL (model ZCU150 through ZCU600) will be pooled together for analysis; which include both study eyes from bilaterally implanted subjects and one study eye from unilaterally implanted subjects. For binocular endpoints (i.e., binocular visual acuity and patient satisfaction questionnaire), only bilaterally

implanted subjects will be included for analysis. Available data will be used for analysis (i.e., no data imputation for missing data).

For the rotational stability endpoint, the primary analysis population will be all eyes implanted with a study toric IOL (model ZCU150 through ZCU600) and with available valid axis data at the 1-week visit.

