## 21.2 PRIMARY ENDPOINT

### PROPORTION OF EYES WITHIN 5 DEGREES OF ABSOLUTE IOL ROTATION

The primary endpoint for this study is the amount of absolute axis rotation from operative axis to the 1-week visit as measured by the photographic axis method. The proportion of eyes with less than or equal to 5 degrees of absolute rotation at 1-week will be reported along with the 95% confidence interval for this proportion.

The clinical success criterion will be that 90% of eyes will have lens rotation of 5 degrees or less at 1-week using the photographic measurement method.

The primary study endpoint is based on objective analysis of study photographs by designated sponsor personnel.

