## **21.5 SAMPLE SIZE CALCULATIONS**

With 200 eyes, the two-sided 95% confidence interval for the proportion of eyes within 5 degrees of absolute rotation at 1-week will extend within 3.0% from the observed proportion assuming an expected proportion of 95% or higher.

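### Section 21 neither scores lenses repositioned before the 1-week photograph nor tests the eyes without valid 1-week data, so the proportion judged against 90% can be biased upward unnoticed

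*Combined protocol and SAP*

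**What the plan says.** Section 21.1 defines the primary rotational population as "all eyes implanted with a study toric IOL (model ZCU150 through ZCU600) and with available valid axis data at the 1-week visit". On missing values it states: "Available data will be used for analysis (i.e., no data imputation for missing data". Section 21.2 sets the criterion: "The clinical success criterion will be that 90% of eyes will have lens rotation of 5 degrees or less at 1-week", measured on photographs that designated sponsor personnel analyse.

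Section 8 gives the enrolment: "Up to 192 subjects (116 bilateral and 76 unilateral) will be enrolled to achieve approximately 200 eyes available for analysis at 1-week". On the margin it says "This accounts for screen failures, drop-out rate and unanalyzable photographs for toric IOL rotation analysis", with no rate for any of the three causes.

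Section 10.7 (Secondary Surgical Interventions) permits repositioning for significant axis misalignment with an unsatisfactory visual result, and asks for a dilated slit lamp photograph of the lens position beforehand. Section 10.2 places the 1-day visit on days 1-2 and the 1-week visit on days 5-14.

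Section 21.3 reports rotation descriptively at 1 day and 3 months, and accountability data. Section 15.1 describes measures to prevent missing data. Section 21 contains no worst-case, tipping-point or other missing-data analysis of the primary endpoint, and no scoring rule for a lens repositioned or removed before the 1-week photograph.

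**The concern.** The endpoint asks whether the lens stays where the surgeon left it. A lens that turns in the first days and is surgically rotated back is a clear failure on that question. Under the current rule the eye can leave the analysis, if no valid 1-week reading exists, or be scored on its axis after correction. Dropping such an eye raises the observed proportion. Scoring it on the corrected axis raises the proportion whenever that axis lies within 5 degrees of baseline.

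Eyes that miss the visit or cannot be read are a second, more uncertain source of bias. Their rotation is unknown and the plan never asks how much it matters. With a fixed criterion and an expected margin of only five percentage points, a modest number of such eyes can decide whether the criterion is met.

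**Working it through.** **Inputs.** 200 eyes and an expected proportion of 95% or higher (Section 21.5); 90% criterion (21.2); 116 bilateral and 76 unilateral subjects at most (Section 8). The number of implanted eyes without valid 1-week data is not given, so it is assumed below and shown as a range.

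**The plan's own figure.** Section 21.5 says "the two-sided 95% confidence interval for the proportion of eyes within 5 degrees of absolute rotation at 1-week will extend within 3.0" percent of the observed proportion. The Wald half-width is 1.96 × √(0.95 × 0.05 / 200) = 3.02%, which reproduces it. At 95% the observed count is 190/200.

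**Size of the margin.** Maximum eyes enrolled: 2 × 116 + 76 = 308, of which 232/308 = 75.3% come from bilateral subjects, matching the 75% target. Margin: 308 − 200 = 108 eyes. Screen failures never receive a study lens, so 108 is a ceiling on post-implant losses.

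**Can repositioning precede the endpoint?** Misalignment can be seen on days 1-2 and the 1-week photograph may be as late as day 14. Nothing in Section 10.7 delays repositioning until after that photograph. The sequence is therefore possible; the documents give no frequency for it.

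**Missing eyes, all counted as failures.** Let m eyes be missing. The overall rate is 190/(200 + m).
- m = 11: 190/211 = 90.05%
- m = 12: 190/212 = 89.6%, below 90%; here 12/212 = 5.7% of implanted eyes are missing
- With 200/200 observed, 23 missing eyes are needed: 200/223 = 89.7%

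**Repositioned eyes scored on the corrected axis.** If k of the 190 successes are such eyes, the rate without them as successes is (190 − k)/200. It is 90.0% at k = 10 and 179/200 = 89.5% at k = 11.

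**Break-even success among missing eyes.** With a fraction f of implanted eyes missing, N = 200/(1 − f). The overall rate equals 90% when success among the missing eyes is (0.9N − 190)/(N − 200).

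| Assumed missing | N implanted | All missing as failures | Break-even success among missing |
|---|---|---|---|
| 10% | 222.2 | 190/222.2 = 85.5% | (200 − 190)/22.2 = 45% |
| 20% | 250 | 190/250 = 76.0% | (225 − 190)/50 = 70% |

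**Dependence on the unknown split.** Assume all 308 eyes are enrolled and 200 are analysed.
- 20% screen failure: about 246 implanted and 46 missing. The all-failure rate is 190/246 = 77.2%. The overall rate falls below 90% if more than (24.6 − 10)/46 = 31.7% of missing eyes fail.
- 30% screen failure: about 216 implanted and 16 missing. The all-failure rate is 190/216 = 88.0%. The break-even failure rate is (21.6 − 10)/16 = 72.5%.

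**The case against.** **The margin is not a missing-data rate.** A reader might infer from 308 and 200 that the plan expects 35% (108/308) of implanted eyes to lack an outcome, with an all-failure rate of 190/308 = 61.7%. The documents do not support that. Section 8 names screen failures among the causes, and 308 follows from an enrolment ceiling. One phrase points the other way: "Each site should implant approximately 24 subjects" (8 × 24 = 192). The Synopsis, however, says enroll for the same number. The 108 stands only as an upper limit.

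**Reversal needs informative loss.** At 10% missing, 55% of the missing eyes must fail, against 5% of those observed; at 20%, 30% must fail. Three operative photographs with a slit lamp back-up (Section 10.6), three good photographs per postoperative visit (Appendix I) and staff training (Section 15.1) should limit losses. This is fair: the calculations show sensitivity and do not predict a reversal.

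**Unreadable images need not relate to rotation.** A reader might infer that every cause of an unusable photograph is linked to rotation. No section says so. Section 8.2 excludes dilated pupils under 6.0 mm, and Appendices C and I describe largely technical faults such as focus, glare and motion blur. The repositioning argument does not depend on this link.

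**A repositioned eye can still be photographed.** True, and Section 10.7 asks for a photograph beforehand. But Section 21 does not direct that this image be used, so the eye may be scored on its corrected axis.

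**Partly covered already.** Rotation summaries at 1 day and 3 months and the accountability data give context. They neither score repositioned eyes nor test the primary result. The change history for version 2.0 mentions wording on repositioned lenses. The difference from the current text is not counted here as an error, but Section 21.1 as it stands contains no such rule.

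**Conclusion.** The point holds in a limited form. As written, the complete-case rule permits an eye that rotated and was repositioned before the 1-week photograph to be excluded or scored on its corrected axis, and either can bias the proportion upward. No planned analysis shows whether the 90% conclusion depends on eyes without data.

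At the planned 95%, the smallest number of missing eyes that could overturn the conclusion is 12, if all failed; with 10% or 20% missing, the break-even success among them is 45% or 70%. These figures rest on 190/200 observed and on assumed missing fractions, because the documents state neither the number of losses nor the frequency of early repositioning. They use the point estimate, since Section 21.2 attaches no confidence bound to the criterion. They do not show that the trial will miss 90%, and they do not make 35% the expected loss. The change should be made, but the primary estimate need not be replaced.

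**What to change.** Keep the complete-case estimate as the headline and add to Sections 21.1 and 21.2:

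1. **Scoring rule.** An eye repositioned or explanted because of rotation or misalignment before its 1-week photograph counts as more than 5 degrees, or is scored on its pre-repositioning photograph; the plan should fix one of the two in advance. It is never scored on its post-repositioning axis. An eye explanted for a reason unrelated to rotation, such as wrong spherical power or a medical complication, is treated as missing.
2. **Tipping-point table** over all implanted eyes, giving the success rate among missing eyes at which the overall rate reaches 90%, and including the case with every missing eye a failure.
3. **Accounting.** The number of implanted eyes without valid 1-week data, by reason: missed visit, unusable operative image, unusable 1-week image, or lens removed.

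Use of 1-day or 3-month photographs for a missing 1-week value should be optional and labelled a sensitivity analysis, restricted to images taken before any repositioning. A 3-month reading may reflect later movement.

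The changes affect analysis only and use data already collected. The cost is a few extra tables and a headline figure that may be slightly lower.
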